7.3.5 Criteria for Removal from Study

Subjects MUST be discontinued from study therapy AND withdrawn from the study for the following reasons:

- The development of unacceptable toxicity
- Pregnancy (Note: pregnancy on study should be reported to BMS within 24 h)
- Any other situation where, in the opinion of the treating physician, continued treatment per protocol, would not be in the best interest of the patient.
- The patient withdraws consent (subject's decision to withdraw for any reason).
- Imprisonment or the compulsory detention for treatment of either a psychiatric or physical (e.g., infectious disease) illness.
- Patient refusal or non-compliance with SBRT (only applicable to groups 2 and 3).
- Study completion

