6. **Other toxicities:** Other IRAEs were reported in 2.3-3.8% (Grade 3/4: 0.8-1.5%, Grade 5: 0-0.3%) of subjects receiving 3mg/kg of ipilimumab and in 5.2% (Grade 3/4: 2.2%; Grade 5: 0.6%) of subjects receiving 10mg/kg of ipilimumab. Ocular inflammation, manifested as Grade 2 or Grade 3 episcleritis or uveitis, was associated with concomitant diarrhea in a few subjects (<1%) and occasionally occurred in the absence of clinically apparent GI symptoms. Other presumed IRAEs reported include, but were not limited to, arthritis/arthralgias, pneumonitis, pancreatitis, autoimmune (aseptic) meningitis, autoimmune nephritis, pure red cell aplasia, noninfective myocarditis, polymyositis, and myasthenia gravis, of which were individually reported for <1% of subjects.

5.1.9. Onset and Resolution of IRAEs:

The median time to onset of Grade 3-5 IRAEs in MDX010-20 and Phase 2 studies was 7 to 9 weeks. The time to onset of IRAEs was comparable between the 3- and 10-mg/kg doses. With the recommended treatment guidelines, the median times to resolution of Grades 3-4 IRAEs was 4 to 8 weeks. The time to resolution of IRAEs was comparable between the 3 and 10-mg/kg doses.

5.1.10. Ipilimumab Dose-dependent Safety Profile:

In MDX010-20, immune-related adverse events (irAEs) occurred in 60% of subjects treated with ipilimumab (3mg/kg) and ≥ Grade 3 events occurred in 12-16%. Treatment related AEs leading to discontinuation of therapy were reported in 9.9% of the ipilimumab monotherapy arm

vs 3.0% of the gp100 monotherapy arm. The most common (>1%) treatment related AEs leading to discontinuation in the ipilimumab monotherapy arm were colitis (2.3%), diarrhea (1.5%), and uveitis (1.5%). In a pooled 3mg/kg group from the Phase 2 studies, 8.1% of subjects reported treatment-related AEs leading to discontinuation. The most common were hypopituitarism (2.7%), colitis (1.8%), and decreased appetite (1.8%). In MDX010-20, treatment-related deaths (defined as a treatment-related AE with an outcome of death, reported at any time during the study) were reported in 4 subjects (3.1%) in the ipilimumab monotherapy group, 8 subjects (2.1%) in the ipilimumab plus gp100 group and 2 (1.5%) subjects in the gp100 monotherapy group.

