7.3.4. Criteria for Permanent Discontinuation of Ipilimumab/BMS-986156 or nivolumab/BMS-986156

Patients who demonstrate signs of progression of disease prior to completion of Ipilimumab/BMS-986156 or Nivolumab/BMS-986156 may continue on trial if determined to provide clinical benefit per the treating physicians and/or PI's discretion.

- Patients will continue to be monitored with visits or phone calls (if patient is unable to arrive) as discussed in section 9.1.3 but will no longer receive further treatment if:
- Patients suffer any of the following adverse events with at least a possible, probable or definite attribution to study treatments:*Adverse event(s) considered related to study treatments as described below:*
 - Any \geq Grade 2 eye pain or reduction of visual acuity that does not respond to topical therapy and does not improve to Grade 1 severity within 2 weeks of starting therapy OR requires systemic treatment;
 - Any \geq Grade 3 bronchospasm or other hypersensitivity reaction;
 - Any other \geq Grade 3 non-skin related adverse event with the exception of laboratory abnormalities;
 - Any Grade 4 laboratory abnormalities, except AST, ALT, or total bilirubin;
 - AST or ALT \geq 8 \times ULN,
 - Total bilirubin \geq 5 \times ULN;
 - Any other Grade 4 adverse event;
 - Drug related toxicity that prevents administration of ipilimumab/BMS-986156 for \geq 21 days or nivolumab/BMS-986156 for 14 days from the scheduled dose
- Any adverse event, laboratory abnormality or intercurrent illness which, in the judgment of the investigator, presents a substantial clinical risk to the subject with continued study drug dosing;
- Subject experiences an allergic/infusion reaction while receiving study drug at a slower infusion rate due to a prior allergic/infusion reaction;
- Any motor neurologic toxicity \geq Grade 3 regardless of causality;

- Any \geq Grade 3 treatment-related sensory neurologic toxicity.
- Drug related toxicity that prevents administration of ipilimumab for \geq 21 days from the scheduled dose

Exceptions to Permanent Discontinuation of ipilimumab dosing:

- Hospitalization for \leq Grade 2 adverse events where the primary reason for hospitalization is to expedite the clinical work-up;

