8.2.3. Follow up - every 2 to 4 months

- Physical examination to include weight and vital signs.
- Physical examination, interim history pertaining to any change from baseline, current medications and treatment-related toxicities. Adverse events will be monitored using the NCI CTCAE Version 4.0.
- Laboratory testing CBC with differential/platelets
- Serum chemistry studies to include sodium, potassium, chloride, carbon dioxide, BUN, creatinine, glucose, magnesium, calcium, phosphorus, albumin, total protein, SGOT (AST) or SGPT (AGT), total bilirubin, alkaline phosphatase and uric acid.
- All appointments after the last cycle of BMS-986156 will allow a window of ± 1 months.
- Radiation oncology follow up appointments will be at the discretion of the treating radiation oncologist. We recommend follow up at 3 and 6 months after the completion of the last cycle of BMS-986156 followed by appointments as per standard of care.

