8.3. Measurement of Effect

1. Response and progression will be evaluated in this study using guidelines proposed by the Immune Related Response Criteria (irRC).
2. The best achieved objective response per irRC criteria (as described below) will consider all imaging conducted after week 1 of cycle 5 for group 1 and 2, or week 2 cycle 3 for group 3 of drug administration. After initial response imaging is obtained, additional imaging will be obtained every 12 weeks (± 4 weeks, or sooner if clinically indicated by treating physician's or PIs discretion) for re-evaluation of treatment response. If in the event that patient receives re-induction, imaging will be obtained after the 4th cycle of re-induction and every 2-3 months thereafter. All imaging obtained during and after re-induction will be considered when obtaining the best achieved objective response for patients who got re-induction treatments.

irRC: Measurable Disease Prior to Therapy (day <1)

Index lesions: Up to 15 index lesions per patient (5 per organ, up to 10 visceral and 5 cutaneous) with minimum size 5 x 5 mm will be accurately measured in two dimensions (two largest perpendicular diameters) on CT or MRI scan (slice thickness no greater than 5 mm) prior to therapy initiation. Lesions measured with calipers by clinical exam may be conducted on lesions no smaller than 10 mm in the smallest dimension. Lesions that cannot be accurately measured with calipers should be recorded as non-measurable.

SBRT-treated index lesions: Defined as all index liver and lung lesions treated by SBRT as part of this protocol.

Non-SBRT-treated index lesions: Defined as all index lesions not treated by SBRT as part of this protocol.

irRC: Index and non-Index Lesions:

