All events occurring during the conduct of a protocol and meeting the definition of a SAE must be reported to the IRB in accordance with the timeframes and procedures outlined in “University of Texas M. D. Anderson Cancer Center Institutional Review Board Policy on Reporting Serious Adverse Events”. Unless stated otherwise in the protocol, all SAEs, expected or unexpected, must be reported to IND Office, regardless of attribution (within 5 working days of knowledge of the event).

Serious adverse events will be captured from the time the patient signs consent until **100 days** after the last dose of drug, whether related or not related to the study drug or any protocol related procedure. Serious adverse events must be followed until clinical recovery is complete and laboratory test have returned to baseline, progression of the event has stabilized, or there has been acceptable resolution of the event.

Additionally, any serious adverse events that occur after the 100 day time period that are related to the study treatment must be reported to the IRB as per MDACC policy. This may include the development of a secondary malignancy.

All life-threatening or fatal events, that are unexpected, and related to the study drug, must have written report submitted within 24 hours (next working day) of knowledge of the event to the Safety Project Manager in the IND Office.

Unless otherwise noted, the electronic SAE application (eSAE) will be utilized for safety reporting to the IND Office and MDACC IRB.

Reporting to the FDA:

- Serious adverse events will be forwarded to the FDA by the IND Sponsor (Safety Project Manager IND Office) according to 21 CFR 312.32.

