10.2.4. Efficacy Analyses

Treatment success and clinical benefit will be defined as irCR or irPR or irSD, assessed using irRC (e.g. the best response obtained by a patient). Clinical benefit will be established as having irCR or irPR or irSD > 6 months. Measurements from all imaging, including those obtained during and after re-induction, will be considered in this analysis. Patients will be continuously evaluated for disease response via imaging until they are removed from the study. For secondary objectives a), b), and c), success probabilities will be estimated for each target separately (liver, lung) along with appropriate 95% confidence intervals. Safety comparisons among the groups will be assessed (primary end points) and efficacy comparisons between groups will be assessed with regard to the irRC outcomes while global, in-field irRC will be used for

hypothesis generating using Pearson chi-squared or Fisher exact tests. For secondary objective d) comparisons will be performed between group 2 and 3 as well as per treatment site (liver, or lung).

1. **Global irRC:** irRC that factors all lesions both index and non-index as outlined in 8.3.
2. **In-Field irRC:** irRC in which only SBRT-treated lesions will be considered and non-index lesions arising inside the SBRT PTV
3. **Out-Field irRC:** irRC in which only non SBRT-treated lesions will be considered and non-index lesions arising outside the SBRT PTV

For the secondary objective comparing the response between the arms. With 20 patients per arm, we would have 80% power using a two-sided 10% alpha with a chi-squared test to detect the following differences in response rates between treatment groups 44% vs 10%, 57% vs 20%, 68% vs 30% and 78% vs 40%. To increase statistical power, we may also combine the patients into a single dataset and fit a logistic regression model with response (CR+PR) as the outcome and SBRT dose, target (liver or lung) among other factors (including but not limited to: number of metastatic disease sites, number of prior treatments, primary cancer histology, age, pre-treatment KPS and Royal Marsden Score) as the predictors.

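### Section 7.3.5 merges stopping treatment with leaving the study for unacceptable toxicity, contradicting 7.3.4, and section 10.2.4 then ends response imaging on removal

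*Combined protocol and SAP*

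**What the plan says.** Section 7.3.5 states "Subjects MUST be discontinued from study therapy AND withdrawn from the study for the following reasons". The first reason listed is "The development of unacceptable toxicity", with no grade or definition and no link to another section. The same list holds pregnancy, physician judgement, withdrawal of consent, detention, refusal of or non-compliance with SBRT (groups 2 and 3), and study completion.

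Section 7.3.4 lists adverse events after which no further treatment is given, among them most related Grade 3 or higher non-skin events and Grade 4 events. Of these patients it says "Patients will continue to be monitored with visits or phone calls (if patient is unable to arrive) as discussed in section 9.1.3". The contents list and the body of section 9 have only 9.1 and 9.2.

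Section 9.1 collects serious adverse events to 100 days after the last dose and adds "Serious adverse events must be followed until clinical recovery is complete", stabilization or acceptable resolution. Section 9 sets a minimum of 100 days for non-serious events.

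On efficacy, section 10.2.4 says "Patients will be continuously evaluated for disease response via imaging until they are removed from the study". Section 8.3 says that best response "will consider all imaging conducted after week 1 of cycle 5 for group 1 and 2", with a separate starting point for group 3.

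**The concern.** Stopping a drug and leaving a trial are different decisions, and 7.3.5 makes them one. The same patient can fall under 7.3.4, which continues monitoring, and under 7.3.5, which ends participation. Nothing says which governs.

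The choice matters because section 10.2.4 ties the end of imaging to removal. If 7.3.5 is followed, response follow-up ends because of an outcome of treatment. The missing response data would then be linked to toxicity, and no rule in the plan says how such patients are classified for response or censored for survival. Secondary objectives d) and e) relate markers to both effectiveness and toxicity, so they depend on having both outcomes in the same patients.

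**Working it through.** **1. The sections side by side, for a patient who stops treatment because of a related Grade 4 event**

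| Section | Treatment | Follow-up |
|---|---|---|
| 7.3.4 | Stops | Monitoring by visit or phone continues; reference leads nowhere |
| 7.3.5, if the event is judged unacceptable | Stops | Patient is withdrawn from the study |
| 9, 9.1, 9.2 | – | Events to 100 days after last dose, serious events to resolution; no exception for withdrawn patients |
| 10.2.4 | – | Response imaging until removal from the study |

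Rows 1 and 2 contradict each other. Row 3 protects safety data whichever of the two is followed. Row 4 makes row 2 decisive for imaging.

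**2. Timing in groups 1 and 2**

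- Combination doses fall on days 1, 22, 43 and 64, so cycle 5 starts on day 64 + 21 = 85. No scan before day 85 counts for best response (8.3).
- Section 5.1.9 says: "The median time to onset of Grade 3-5 IRAEs in MDX010-20 and Phase 2 studies was 7 to 9 weeks". That is day 7 × 7 = 49 to day 9 × 7 = 63.
- Gap to the first scan that could count: 85 − 63 = 22 days to 85 − 49 = 36 days.
- By day 49 a patient on schedule has had three doses, and in group 2 SBRT ended on day 32 or day 40. The response set (10.1, 10.2.1) asks for at most two drug treatments and half the radiation, so this patient is in it.

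A patient removed at that point is in the denominator with no countable scan. Removal soon after day 85 also costs data: irCR and irPR need confirmation at least 4 weeks later (8.5.1), and clinical benefit needs more than 6 months (10.2.4).

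**3. How many patients**

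The plan gives no rate for unacceptable toxicity. The nearest figures are discontinuations for treatment-related events:

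- Ipilimumab 3 mg/kg: 8.1% (pooled Phase 2) and 9.9% (MDX010-20), section 5.1.10. Applied to groups 1 and 2: 40 × 0.081 = 3.24 and 40 × 0.099 = 3.96.
- Nivolumab + BMS-986156: 4 related events leading to discontinuation in 225 subjects, section 3.1.4, counted here as 4 patients. Applied to group 3: 20 × 4/225 = 0.36.
- Total: 3.24 + 0.36 = 3.6 to 3.96 + 0.36 = 4.3 of 60, about 2 per ipilimumab group of 20.

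**4. What that does to the response results**

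The plan's own figure first: 80% power with 20 per arm at two-sided 10% alpha (10.2.4). With

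power = Φ{ [|p1 − p2| − 1.645 √(2p̄(1 − p̄)/n)] / √([p1(1 − p1) + p2(1 − p2)]/n) }

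the first pair (44% v 10%) gives (0.34 − 0.231)/0.130 = 0.84, so power is 0.800. The other three pairs give 0.794, 0.794 and 0.807. The figure reproduces.

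With 2 of 20 lost in each of groups 1 and 2 (n = 18), power is 0.760, 0.754, 0.754 and 0.767: a fall of about 4 points.

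The larger effect is on the estimate. If 10% of the 18 observed patients respond and the 2 others have no outcome, the rate in all 20 lies between 0.10 × 18/20 = 9% and (0.10 × 18 + 2)/20 = 19%.

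**The case against.** The best counter-argument is that section 9 already protects the data that matter most. Its windows run from the last dose, not from study exit. It requires follow-up of non-serious events that cause discontinuation of study drug, and related serious events stay reportable after 100 days. Everyone given any study drug is evaluable for toxicity. The event that triggers removal is already on record, so DLT counts are untouched. All of this stands. A reader might infer from 7.3.5 that safety data are lost, and the documents do not support that: such loss needs a site to read withdrawal as ending all collection.

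Second, being on the 7.3.5 list does not always end follow-up. Study completion is on it, yet 8.1.4 prescribes up to a year of monitoring afterwards. Pregnancy is on it, yet section 9 requires follow-up. This shows that the word is used loosely. It does not resolve the conflict with 7.3.4, and 10.2.4 still stops imaging at removal.

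Third, the 9.1.3 reference may be stale numbering, like the references to 9.4 in 8.1.1 and 9.5 in 8.3. Those two make sense as 8.4 and 8.5. The same shift sends 9.1.3 to 8.1.3, which lists pre-study tests, so a site cannot recover the intended schedule that way.

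Fourth, the late start of countable imaging comes from 8.3, and the between-group tests are labelled exploratory. Both are true. The first means that 7.3.5 creates the gap only in combination with 8.3 and 10.2.4. The second makes the power loss minor, but the descriptive response rates are still affected.

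**Conclusion.** The contradiction between 7.3.5 and 7.3.4 is real and should be corrected. Followed as written, 7.3.5 with 10.2.4 ends response imaging because of toxicity, and may end survival and late follow-up. Size: about 4 of 60 patients, assuming that the quoted discontinuation rates carry over and that each such patient is withdrawn. No rate exists for ipilimumab with BMS-986156, so the number could be higher. The direction of any bias is unknown.

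Four stronger readings are tempting and not supported:

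- **About 20 of 60 affected.** This applies the 34% Grade 3 rate of the earlier ipilimumab + SBRT trial (section 3.3) to everyone (60 × 0.34 = 20.4). It treats every Grade 3 event as a withdrawal, although the same text calls most of them self-limiting and gives 6% DLTs. It also applies an ipilimumab rate to group 3, which receives none.
- **The same conflict for patients who refuse SBRT.** Section 7.3.4 does not mention them. Those with less than half the radiation are already outside the response set, and those who decline all of it never enter the survival analysis, which starts at the first fraction.
- **First contact after event collection has closed.** Visits every 2 to 4 months with "All appointments after the last cycle of BMS-986156 will allow a window of ± 1 months" could put first contact near day 150, against 100 days. But the 100 days define which events count, and a later contact can still record them. For non-serious events 100 days is a minimum.
- **A known survival bias.** The hazard ratio of 0.23 in section 5.1.13 is unadjusted and comes from ipilimumab 10 mg/kg plus dacarbazine. It does not show the direction here.

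**What to change.** Reconcile 7.3.5 with 7.3.4, section 9 and 10.2.4 in one wording amendment:

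- Separate discontinuation of study therapy from withdrawal from the study.
- State that patients who stop treatment for toxicity, physician decision or SBRT non-compliance stay in the existing follow-up of 8.1.4 and 8.2.3 for imaging, safety and survival, unless they withdraw consent. Leave pregnancy and detention under their own provisions.
- Say how unacceptable toxicity relates to the list in 7.3.4.
- Replace the 9.1.3 reference with the section that holds the follow-up schedule.
- Amend 10.2.4 so that imaging does not end when treatment stops. State how a patient in the response set with no countable scan is classified, and how survival is censored.

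No treatment-stopping rule changes, and sample size and power stay as stated. The cost is the amendment and some extra contacts and scans in patients off treatment, about four at the rates above. Phone contact is already allowed.

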7.4. Immune Related Adverse Events (IRAEs): Definition, Monitoring and Treatment

Blocking CTLA-4/PD-1/GITR function may permit the emergence of auto-reactive T cells and resultant clinical autoimmunity. Rash/vitiligo, diarrhea/colitis, uveitis/episcleritis, hepatitis and hypopituitarism were drug-related, presumptive autoimmune events, now termed IRAEs.

For the purposes of this study, an IRAE is defined as an AE of unknown etiology, associated with drug exposure and is consistent with an immune phenomenon. Efforts should be made to rule out neoplastic, infectious, metabolic, toxin or other etiologic causes prior to labeling an AE an IRAE. Serological, immunological, and histological (biopsy) data should be used to support the diagnosis of an immune-mediated toxicity. Suspected IRAEs must be documented on an AE or SAE form.

Patients should be informed of and carefully monitored for evidence of clinically significant systemic IRAE (e.g., systemic lupus erythematosus-like diseases) or organ specific IRAE (e.g., rash, colitis, uveitis, hepatitis or thyroid disease). If an IRAE is noted, appropriate work-up (including biopsy if possible) should be performed, and steroid therapy may be considered if clinically necessary.

It has been reported that systemic corticosteroid therapy does not seem to have an attenuating effect on ipilimumab activity (28). However, administration of a prophylactic corticosteroid, budesonide, did not impart any clinical benefit in patients treated with ipilimumab (29). If utilized, corticosteroid therapy should be individualized for each patient. Prior experience suggests that colitis manifested as Grade \geq 3 diarrhea requires corticosteroid treatment.

7.4.1 Management Algorithms for Immuno-oncology Agents

Immuno-oncology (I-O) agents are associated with AEs that can differ in severity and duration from AEs caused by other therapeutic classes. Ipilimumab, Nivolumab and BMS-986156 are considered I-O agents in this protocol. Early recognition and management of AEs associated with I-O agents may mitigate severe toxicity. Management algorithms that have been developed from

extensive experience with nivolumab to assist Investigators in assessing and managing the following groups of AEs:

- Gastrointestinal
- Renal
- Pulmonary
- Hepatic
- Endocrinopathies
- Skin
- Neurological

The algorithms recommended for utilization in this protocol are included in Appendix B.

7.4.2. Treatment of Drug-related Infusion Reactions

If BMS-986156 and nivolumab found to be immunogenic and induce infusion or hypersensitivity reactions, it might manifest with fever, chills, rigors, headache, rash, pruritus, arthralgias, hypo- or hypertension, bronchospasm, or other symptoms. All Grade 3 or 4 infusion reactions should be reported within 24 hours to the BMS Medical Monitor and reported as an SAE if criteria are met. Infusion reactions should be graded according to NCI CTCAE v4.03 guidelines.

Treatment recommendations are provided below and may be modified based on local treatment standards and guidelines as appropriate:

For Grade 1 symptoms: (Mild reaction; infusion interruption not indicated; intervention not indicated)

Remain at bedside and monitor subject until recovery from symptoms. The following prophylactic premedications are recommended for future infusions: diphenhydramine 50 mg (or equivalent) and/or acetaminophen/paracetamol 325 to 1000 mg at least 30 minutes before additional study drug administrations.

For Grade 2 symptoms: Moderate reaction requires therapy or infusion interruption but responds promptly to symptomatic treatment [e.g., antihistamines, non-steroidal anti-inflammatory drugs, narcotics, corticosteroids, bronchodilators, IV fluids]; prophylactic medications indicated for ≤ 24 hours.

- Stop the nivolumab infusion, begin an IV infusion of normal saline, and treat the subject with diphenhydramine 50 mg IV (or equivalent) and/or paracetamol 325 to 1000 mg (acetaminophen); monitor subject until resolution of symptoms.
- Bronchodilator or corticosteroid therapy may also be administered as appropriate.
- The infusion may be restarted at 50% of the original infusion rate when symptoms resolve; if no further complications ensue after 30 minutes, the rate may be increased to 100% of the original infusion rate. Monitor subject closely.
- The amount of study drug infused must be recorded on the CRF.
- If symptoms recur, then no further nivolumab, as the case may be, will be administered at that visit.
- The following prophylactic premedications are recommended for future infusions: diphenhydramine 50 mg (or equivalent) and/or paracetamol 325 to 1000 mg (acetaminophen) should be administered at least 30 minutes before additional nivolumab administrations. If

necessary, corticosteroids (up to 25 mg of SoluCortef or equivalent) may be used.

Late-occurring symptoms: In the case of late-occurring hypersensitivity symptoms (e.g., appearance of a localized or generalized pruritus within 1 week after treatment), symptomatic treatment may be given (e.g., oral antihistamine, or corticosteroids).

For Grade 3 or Grade 4 symptoms (Severe reaction, Grade 3: prolonged [e.g., not rapidly responsive to symptomatic medication and/or brief interruption of infusion]; recurrence of symptoms following initial improvement; hospitalization indicated for other clinical sequelae [e.g., renal impairment, pulmonary infiltrates]; Grade 4: life-threatening; pressor or ventilatory support indicated).

Immediately discontinue study drug infusion. Begin an IV infusion of normal saline, and treat the subject as follows. Recommend bronchodilators, epinephrine 0.2 to 1 mg of a 1:1,000 solution for subcutaneous administration or 0.1 to 0.25 mg of a 1:10,000 solution injected slowly for IV administration, and/or diphenhydramine 50 mg IV with methylprednisolone 100 mg IV (or equivalent), as needed. Subject should be monitored until the Investigator is comfortable that the symptoms will not recur. Study drug will be permanently discontinued. Investigators should follow their institutional guidelines for the treatment of anaphylaxis. Remain at bedside and monitor subject until recovery from symptoms. In the case of late-occurring hypersensitivity symptoms (e.g., appearance of a localized or generalized pruritus within 1 week after treatment), symptomatic treatment may be given (e.g., oral antihistamine, or corticosteroids).

